7. STATISTICAL CONSIDERATIONS

7.1. Adjustments for Covariates and Factors to be Included in Analyses

The following covariates and factors will be used in the analyses. For details of their inclusion in the models, see the specific analysis section.

- Fixed effects: treatment (RPL554 0.375 mg, RPL554 0.75 mg, RPL554 1.5 mg, RPL554 3 mg, Placebo), visit (Day 1, Weeks 1, 2, 3 and 4), visit*treatment, actual reversibility strata (reversible, non-reversible)
- Random effect – patient
- Covariate – baseline

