16.1.2. Primary Analysis of Primary Efficacy Variables

Peak FEV_1 will be summarised as actual value at Week 4 and change from baseline FEV_1 to peak FEV_1 at Week 4 using descriptive statistics for all treatment groups.

Peak FEV_1 will be computed as the maximum value in the 3 hours after dosing. Baseline FEV_1 is the latest measurement taken before study drug on the day of first dosing, i.e. 30 minutes pre-dose at Day 1.

The primary objective of this study is to test the hypothesis that there is a difference between different dose levels of study treatment (RPL554) in comparison with placebo, all administered by nebulizer and added on to tiotropium. The change from baseline FEV_1 to peak FEV_1 will be compared between the treatments using a mixed model for repeated measures (MMRM) with fixed effects for treatment, visit and treatment by visit interaction, patient as random effect and baseline as covariate. An unstructured covariance structure will be used to model the within-patient errors. If the model does not converge a compound symmetry covariance structure will be used. Kenward-Roger method will be used to estimate the model degrees of freedom.

Treatment comparisons will be summarised using mean effect differences with 95% CI and associated 2-sided p-values.

Firstly, RPL554 treatments will be compared to placebo using a closed testing procedure. The testing will begin with the highest dose (3 mg) compared to placebo. If found statistically significant then the lower dose (1.5 mg) will be compared to placebo. If found significant then the next lower dose will be compared to placebo until either all doses are compared to placebo, or a result is found to be non-significant and therefore the comparison ends. Secondly, the doses will be compared in a pairwise fashion as shown in Table 2, below.

Document: ...\\Verona_Pharma\\RPL554\\BZA48916\\Biostatistics\\Documentation\\SAP\\Verona CO-205 SAP v1.0

Author: [REDACTED] Version Number: V1.0

Version Date: 05DEC2019

Template No.: CS_TP_BS016 Revision 5

Reference: CS_WI_BS005

Effective Date: 01Apr2018

Table 2: Pairwise comparison between the RPL554 treatment groups:

RPL554 dose	[REDACTED]	[REDACTED]	[REDACTED]	[REDACTED]	[REDACTED]	[REDACTED]
	[REDACTED]	[REDACTED]	[REDACTED]	[REDACTED]	[REDACTED]	[REDACTED]
	[REDACTED]	[REDACTED]	[REDACTED]	[REDACTED]	[REDACTED]	[REDACTED]
	[REDACTED]	[REDACTED]	[REDACTED]	[REDACTED]	[REDACTED]	[REDACTED]

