16.6. Interim Analysis

To check the assumptions in the sample size calculation, as detailed in Section 9.5 of the study protocol, a blinded sample size-re-estimation is planned after 125 patients who have been randomized, have collected sufficient data after intake of study treatment to compute any of the FEV₁ parameters and either completed the study or had early termination. Analyses will be based on data that is as clean as possible at the time of the data cut-off.

Two different models will be fitted to the data and both will estimate blinded standard deviation which will be compared to the standard deviation assumption of 200 mL included in the original sample size calculation. Using each of these blinded estimates of the standard deviation, the original sample size calculation, based on a two-sample t-test, will be repeated for each of the following scenarios.

- Calculation 1 – unknown sample size (per treatment group), known detectable treatment difference (93 mL) and power (80%)
- Calculation 2 – unknown power (%), known detectable treatment difference (93 mL) and sample size (73 per treatment group)
- Calculation 3 – Unknown detectable treatment difference (mL), known power (80%) and sample size (73 per treatment group)

The ANCOVA analysis will be performed on the following endpoints. The MMRM analysis will be performed for the first endpoint only:

- Change from baseline FEV₁ to peak FEV₁ at Visit 6
- Change from baseline FEV₁ to average AUC_{0-3h} FEV₁ at Visit 6
- Change from baseline FEV₁ to average AUC_{0-12h} FEV₁ at Visit 6
- Change from baseline FEV₁ to morning trough FEV₁ at Visit 6

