16.6.2. Blinded MMRM analysis

To analyse the change from baseline FEV₁ to peak FEV₁, an MMRM approach will be used with a fixed factor for visit, patient as a random effect, and the baseline result as a covariate. An unstructured covariance structure will be used to model the within-patient errors. If the model does not converge a compound symmetry covariance structure will be used. Kenward-Roger method will be used to estimate the model degrees of freedom.

Sample size calculation is based on the number of patients with available data at Visit 6/week 4 included in the analysis, therefore any assessment of sample size based on MMRM should also consider the drop-out rate observed in the study.

The MMRM model will use the square root of variance representing Visit 6/Week 4 taken from variance-covariance matrix to estimate the blinded standard deviation.

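### If the primary MMRM does not converge, the only fallback is equal-variance compound symmetry, which mis-sizes the Week 4 standard error when the Week 4 variance differs from the visit average; the random patient effect beside the unstructured matrix is redundant

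*SAP*

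**What the plan says.** SAP 16.1.2 analyses change from baseline to peak FEV₁ with an MMRM: fixed effects for treatment, visit and their interaction, then "patient as random effect and baseline as covariate. An unstructured covariance structure will be used to model the within-patient errors". It continues: "If the model does not converge a compound symmetry covariance structure will be used". It adds that the "Kenward-Roger method will be used to estimate the model degrees of freedom".

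SAP 7.1 has the entry "Random effect – patient" and five visits (Day 1 and Weeks 1 to 4). Protocol 9.4.5 likewise makes patient random while structuring the covariance by visit. SAP 16.2.2 reuses the model for the secondary endpoints, and SAP 7.4 fits it separately within subgroup strata.

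The blinded MMRM in SAP 16.6.2 has "a fixed factor for visit, patient as a random effect, and the baseline result as a covariate", with the same unstructured matrix and the same fallback. For the SD, "The MMRM model will use the square root of variance representing Visit 6/Week 4 taken from variance-covariance matrix". SAP 16.6 says that the estimates are "compared to the standard deviation assumption of 200 mL included in the original sample size calculation".

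No other covariance structure is named in either document.

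**The concern.** There are two separate issues.

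- **Redundancy.** An unstructured matrix already holds every variance and covariance across visits. A random patient effect adds the same constant to all of them, so the data cannot separate the two. This is an avoidable numerical risk, and it leaves open which matrix supplies the Week 4 variance in the blinded review.
- **Fallback.** If the fit fails, the plan goes from 15 parameters to 2 in one step and forces one variance on all visits. The primary contrast is at a single visit, so its standard error then depends on variances at the other four. Doses are tested in order from 3 mg downwards, and one non-significant result stops the sequence. A mis-sized standard error could therefore change which doses are declared effective.

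In the blinded review, the fallback would replace the Week 4 variance that SAP 16.6.2 asks for with an all-visit pool, and that figure is set against the 12% and 20% limits in SAP 4.2.

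**Working it through.** **Inputs.** SD 200 mL, difference 93 mL, two-sided 5%, 73 evaluable per arm (protocol 9.5); five visits (SAP 7.1). Visit-specific SDs and within-patient correlations are not in the documents, so those below are assumptions.

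**1. The plan's own figure.** SE = 200 × √(2/73) = 33.1 mL. The normal approximation gives n = 73 and power 80.2%; the t-test gives 79.7% at n = 73. The sample size is reproduced.

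**2. Parameter count.** Unstructured over five visits: 5 × 6 / 2 = 15. Adding a patient variance g gives 16. The total covariance is V = gJ + R, where J is a matrix of ones, so any g paired with R = V − gJ gives the same V. The rank is 15 of 16. For endpoints with two post-baseline visits (SGRQ-C, TDI, PGAC) it is 3 of 4. Compound symmetry plus a patient effect has rank 2 of 3.

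**3. Effect on a converged fit.** The Week 4 contrast and its standard error depend only on V, which is unchanged: SE 33.1 mL with or without the patient term.

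**4. Effect of the fallback.** With complete data, compound symmetry uses the mean of the five visit variances. So:

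- r = √(mean SD²) / SD at Week 4
- type I error = 2 × (1 − Φ(1.96 r))
- power ≈ Φ(93/33.1 − 1.96 r)

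For 180, 185, 190, 195, 200 mL: mean SD² = 36,150, root 190.1, r = 0.951, model SE = 31.5 mL, type I error 6.2%. For 240, 230, 220, 210, 200 mL: mean SD² = 48,600, root 220.5, r = 1.102, model SE = 36.5 mL, type I error 3.1%, power 74%.

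| Assumed SD, Day 1 to Week 4 (mL, linear) | r | Type I error per comparison |
|---|---|---|
| 180 to 200 | 0.951 | 6.2% |
| 190 to 200 | 0.975 | 5.6% |
| 200 throughout | 1.000 | 5.0% |
| 210 to 200 | 1.025 | 4.5% |
| 220 to 200 | 1.051 | 4.0% (power 77%) |
| 240 to 200 | 1.102 | 3.1% (power 74%) |

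The condition is a Week 4 variance that differs from the visit average, not unequal variances as such. SDs of 220, 178, 220, 178, 200 mL are unequal, yet √(200,168 / 5) = 200.1 and r = 1.00.

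**5. Simulation check.** REML in Python, 5 × 80 patients, 10% dropout, correlation 0.7 (exchangeable or AR(1)), 1,000 trials × 4 contrasts, Monte Carlo error about 0.5 percentage points; not SAS and without Kenward-Roger.

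- Compound symmetry: type I error 6.2–6.9% (180 to 200), 5.1% (equal SDs), 3.3–3.4% with power 73–75% (240 to 200).
- Heterogeneous Toeplitz, AR(1) and compound symmetry: 4.8–5.6% in every scenario, against 5.1–5.6% for unstructured.

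**6. Blinded review.** Assumed SDs 216, 222, 228, 234, 240 mL: √(260,280 / 5) = 228.2 mL, which is +14% over 200, while Week 4 itself is +20%. Under SAP 4.2 this moves the MMRM result from mandatory re-estimation (20% or more) to the discretionary 12–20% band. At SD 240 mL, 73 per arm gives 64% power by t-test, and 80% needs 106 per arm.

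**7. Which matrix.** Take a total Week 4 SD of 200 mL, SDs rising from 160 mL and correlation 0.7. Patient variances of 0, 5,000, 10,000 and 15,000 mL² all give the same V with a valid R. The Week 4 SD read from R alone would be √40,000 = 200, √35,000 = 187, √30,000 = 173 or √25,000 = 158 mL. Only the total is well defined.

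**The case against.** The ordinary reading is probably the intended one. A covariance structured by visit, and a Week 4 variance taken from one matrix and compared with a total SD of 200 mL, both fit patient as the repeated-measures subject. The text does not say so, but on that reading the redundancy disappears. This largely stands.

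Two stronger inferences are tempting, and neither is supported.

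- **That the literal model biases the primary result or will not converge.** A converged fit is unaffected, and failure in SAS is not shown. In 200 simulated trials (Python REML, about 10% dropout, no lower bound on the patient variance) the 16-parameter model converged every time.
- **That the singular information matrix spoils Kenward-Roger.** The patient-variance derivative is a linear combination of the unstructured ones, so the choice of inverse does not matter. In those 200 trials the Kenward-Roger standard error and degrees of freedom for the Week 4 contrast matched those of plain unstructured to within 1e-7.

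It is also fair that the plan does pre-specify a fallback, that small drifts matter little, and that safeguards exist. The Week 4 ANCOVA in SAP 16.5 and the blinded ANCOVA SD in SAP 16.6.1 do not depend on the MMRM covariance, and protocol 9.4.9 requires an amendment before any sample size increase. These limit the harm without removing it. The sensitivity ANCOVA uses LOCF and is not the primary test, and SAP 4.2 does not say which of the two blinded SDs governs. What remains is the fallback itself.

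**Conclusion.** The point holds as a cheap improvement, not as a demonstrated error in the primary analysis. The random patient effect, taken literally, is redundant and needs clarifying. The substantive weakness is that the sole fallback discards the visit-specific variance that a single-visit contrast needs.

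Harm requires both non-convergence, which is not shown to be likely, and a Week 4 variance away from the visit average. If both occur, the standard error is too small when Week 4 is the more variable and too large when it is the less variable. On the assumed linear drifts of 10 to 40 mL, type I error per comparison lies between 3.1% and 6.2%, and power falls to 74% at worst. With equal variances there is no effect. The blinded-review example (+14% read for a true +20%) is likewise an assumption, and the ANCOVA SD reported beside it would still target the Week 4 value.

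**What to change.** - **SAP 7.1, 16.1.2 and 16.6.2:** state that patient is only the repeated-measures subject and delete the separate random effect. Keep the unstructured matrix across visits with Kenward-Roger.
- **SAP 16.1.2 and 16.6.2:** replace the compound symmetry fallback with a pre-specified order of structures that keep visit-specific variances, for example heterogeneous Toeplitz, then heterogeneous AR(1), then heterogeneous compound symmetry.
- **SAP 16.6.2:** define the SD as the square root of the Week 4 diagonal of the total (marginal) covariance.
- **SAP 3.3:** an entry is needed only if protocol 9.4.5 meant the random patient effect literally.

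The cost is wording and model code, with no change to data, visits or sample size. The fallbacks estimate 6 to 9 covariance parameters instead of 2. A wrong correlation pattern costs a little precision: simulated SE 34.1 against 33.0 mL for heterogeneous compound symmetry when the truth is AR(1). That is why the more flexible Toeplitz structure comes first.

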16.2. Secondary Efficacy

The secondary efficacy endpoints include:

- Change from baseline FEV₁ to average AUC_{0-3h} FEV₁ on Day 1 and at Weeks 1 to 4
- Change from baseline FEV₁ to average AUC_{0-12h} FEV₁ on Day 1 and at Week 4
- Change from baseline FEV₁ to peak FEV₁ on Day 1 and at Weeks 1 to 3
- Change from baseline FEV₁ to morning trough FEV₁ at Weeks 1 to 4
- Change from baseline (i.e., mean over the last 7 days of run-in) to the mean weekly values over Weeks 1 to 4 in COPD symptoms, as measured by daily diary (E-RSTM:COPD)
- Change from baseline in the SGRQ-C questionnaire at Weeks 2 and 4
- TDI questionnaire at Weeks 2 and 4
- PGAC questionnaire at Weeks 2 and 4
- Change from baseline (i.e., mean over the last 7 days of run-in) to the mean weekly values over Weeks 1 to 4 in the number of puffs of rescue medication
- Change from baseline FVC to peak FVC on Day 1 and at Week 4
- Change from baseline FVC to average AUC_{0-3h} FVC on Day 1 and at Week 4
- Change from baseline FVC to average AUC_{0-12h} FVC on Day 1 and at Week 4
- Change from baseline FVC to morning trough FVC at Weeks 1 to 4
- Proportion of patients with an improvement from baseline in SGRQ-C total score of 4 or more

Document: ...\\Verona_Pharma\\RPL554\\BZA48916\\Biostatistics\\Documentation\\SAP\\Verona CO-205 SAP v1.0

Author: [REDACTED] Version Number: V1.0

Version Date: 05DEC2019

Template No.: CS_TP_BS016 Revision 5

Reference: CS_WI_BS005

Effective Date: 01Apr2018

- Trough plasma concentration of tiotropium on Day 1 and at Week 2, and trough plasma concentration of RPL554 at Week 2
- Safety and tolerability:
 - Continuous monitoring of AEs
 - Laboratory safety tests (hematology, blood chemistry and urinalysis)
 - 12-lead ECG (including the QT interval corrected for heart rate using Friderica's formula (QTcF) and heart rate), supine vital signs (blood pressure and pulse rate)

16.2.1. Secondary Efficacy Variables & Derivations

16.2.1.1. PULMONARY FUNCTION TESTS

16.2.1.1.1. SPIROMETRY

Spirometry (FEV₁ and FVC) will be performed at Screening and the following time points during each treatment:

- Day 1 and Week 4 (End of Study): 30 minutes pre-dose; 30 minutes and 1, 2, 4, 6, 8 and 12 hours post-dose.
- Week 1 – Week 3: 30 minutes pre-dose; 30 minutes and 1, 2 and 3 hours post-dose.

At each time point, three acceptable measurements of FEV₁ and FVC will be recorded and the highest reading from each time point will be used in all summaries and analyses. Each measurement will be graded based on the quality of the measurement. Grades “Acceptable” and “Borderline Acceptable” will be used in the analyses, as these will indicate usable measurements. Grade “Unacceptable” will not be used in the analysis, as the measurement will be identified as poor quality.

Morning trough FEV₁ is the last value collected prior to the morning dose.

Peak, average and trough FEV₁ and FVC will be summarized as actual value and change from baseline FEV₁ and FVC (e.g. change from baseline FEV₁ to peak/average/trough FEV₁).

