Review symptom e-diary			X	X	X	X	X	
SGRQ-C, BDI/TDI & CAT questionnaires			X		X		X	
Pre-dose PK blood sample ⁽ⁱ⁾			X		X			
Randomization			X					
Administer study treatments (tiotropium & double-blind study medication) ^(k)			X ^(l)	X	X	X	X	
Nebulization inhalation training			X					
Dispense study medication & nebulizer			X	X	X	X		
Dispense compressor			X					
Collect study medication & nebulizer				X	X	X	X	
Study treatment compliance (including tiotropium)			X	X	X	X	X	
Administer PGAC questionnaire					X		X	
Collect compressor							X	
Collect symptom e-diary								X

Abbreviations: BDI/TDI=Baseline Dyspnea Index/Transition Dyspnea Index; CAT=COPD assessment test; d=days; ECG=electrocardiogram; ET=early termination; mins=minutes; mMRC=modified Medical Research Council; QTcF=QT interval corrected using Fridericia's formula; PGAC=Patient Global Assessment of Change; PK=pharmacokinetics; SGRQ-C=St George's Respiratory Questionnaire-COPD specific

- (a) A second canister of albuterol may be dispensed during the study if necessary
- (b) Body weight only at Visit 6
- (c) ECG at Visits 2, 3 and 6 is performed pre-dose and 2 hours post-dose
- (d) Vital signs at Visits 2 and 6 are measured pre-dose and 30 minutes, 1, 2, 4, 6, 8 and 12 hours post-dose
- (e) Vital signs at Visits 3, 4 and 5 are measured pre-dose and 30 minutes, 1, 2 and 3 hours post-dose
- (f) Serum pregnancy test at Visit 1; urine pregnancy test at Visits 1, 2 and 6
- (g) Inspiratory capacity is performed via slow maneuver prior to forced efforts at Visits 2 and 6, 30 minutes pre-dose and 2 hours post-dose.
- (h) Forced efforts at Visits 2 and 6 are performed 30 minutes pre-dose (after inspiratory capacity), followed by 30 minutes and 1, 2, 3, 4, 6, 8 and 12 hours post-dose
- (i) Spirometry at Visits 3, 4 and 5 is performed 30 minutes pre-dose, followed by 30 minutes and 1, 2 and 3 hours post-dose

Visit	Visit 0 Pre-Screen	Visit 1 Screening (Week -2 ±1 d)	Visit 2 Randomiza- tion	Visit 3 (Week 1 ±1 d)	Visit 4 (Week 2 ±1 d)	Visit 5 (Week 3 ±1 d)	Visit 6 End of Study (Week 4 ±1 d or ET)	Telephone Follow-up (1 week after Visit 6 ±2 d)

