6.4 Treatment Period: Visit 2 (Randomization)

Patients must withhold all medications described in Section 5.9 prior to treatment in accordance with the washout times provided. If not, the visit must be rescheduled so as to occur within the permitted windows. All restrictions defined in Section 6.1 should also be adhered to.

6.4.1 *Pre-dose Assessments*

- The following assessments will be performed prior to dosing: Inclusion/Exclusion Criteria, including randomization criteria (see Section 4.1 to Section 4.3)
- Concomitant medications; confirm that medications were withheld as required
- Review of e-diary to confirm compliance with the device
- Assessment of tiotropium compliance
- mMRC questionnaire
- Questioning for adverse events
- Urine pregnancy test (females of childbearing potential only)
- 12-lead ECG
- Vital signs
- SGRQ-C, BDI and CAT questionnaires
- Blood sample for tiotropium PK measurement
- Slow spirometry (to obtain inspiratory capacity), performed 30 (± 10) minutes pre-dose
- Forced spirometry, performed following completion of slow maneuver
- Inhalation training
- Administration of tiotropium

6.4.2 *Study Medication Administration*

Patients will be administered either RPL554 or placebo by the unblinded study staff member according to the randomization scheme, and again approximately 12 hours later upon completion of the assessments listed below.

Note: If possible, the unblinded study staff member should administer both doses at Visit 2, but if this cannot be arranged for the evening dose it may be done by a blinded staff member provided that he/she does not directly observe the patient pouring the suspension into the nebulizer.

6.4.3 *Post-dose Assessments*

The following assessments will be performed, at the times indicated relative to the end of dosing:

- 12-lead ECG at 2 hours (± 10 minutes)
- Vital signs at 30 minutes and 1, 2, 4, 6, 8 and 12 hours (± 10 minutes)
- Spirometry: Forced efforts at 30 (± 10) minutes and 1, 2, 3, 4, 6, 8 and 12 hours (the latter assessments all ± 15 minutes). At 2 hours post-dose, a slow IC maneuver will precede the forced efforts
- Questioning for adverse events

Patients completing the visit will be dispensed a compressor, nebulizer, open label tiotropium and a box of double-blind study medication. They will demonstrate their ability to use the study medication and nebulizer by administering the evening dose while in the clinic that day. They will be instructed/reminded of the following:

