3.2. Schedule of Events

Schedule of events can be found in Section 6.0 of the study protocol.

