3.3. Changes to Analysis from Protocol

No changes to the analysis outlines in the protocol are planned.

Document: ...\\Verona_Pharma\\RPL554\\BZA48916\\Biostatistics\\Documentation\\SAP\\Verona CO-205 SAP v1.0

Author: [REDACTED] Version Number: V1.0

Version Date: 05DEC2019

Template No.: CS_TP_BS016 Revision 5

Reference: CS_WI_BS005

Effective Date: 01Apr2018

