16. EFFICACY OUTCOMES

16.1. Primary Efficacy

16.1.1. Primary Efficacy Variables & Derivations

The primary endpoint is the change from baseline FEV_1 to peak FEV_1 (maximum value following dose during the first 3 hours) at Week 4 (after 4 weeks of treatment).

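### SAP 16.2.1.1.1 omits the protocol's 3 h spirometry reading on Day 1 and at Week 4, and the SAP does not settle the divisor for a truncated AUC (minor)

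*SAP*

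**What the plan says.** **Time points.** For Day 1 and Week 4, SAP 16.2.1.1.1 lists "Day 1 and Week 4 (End of Study): 30 minutes pre-dose; 30 minutes and 1, 2, 4, 6, 8 and 12 hours post-dose". For Weeks 1 to 3 it lists "30 minutes pre-dose; 30 minutes and 1, 2 and 3 hours post-dose", so the 3 h reading is kept there. For the same Day 1 and Week 4 visits, note (h) to protocol Table 4 has the pre-dose reading "followed by 30 minutes and 1, 2, 3, 4, 6, 8 and 12 hours post-dose", and protocol 6.4.3 (Visit 2) and 6.6.3 (Visit 6) repeat that schedule.

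**Status of the list.** SAP 16.2.1.1.1 adds that "the highest reading from each time point will be used in all summaries and analyses". SAP 3.3 states that "No changes to the analysis outlines in the protocol are planned", and SAP 3.2 that "Schedule of events can be found in Section 6.0 of the study protocol".

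**Derivations.** SAP 16.1.1 defines the primary peak as the "maximum value following dose during the first 3 hours", and 16.1.2 repeats this. SAP 16.3.1 refers the reader to 16.2.1.1.1 for the definition of peak FEV1, but that section contains no formula for it. SAP 16.2.1.1.2 obtains the average effect by dividing the AUC by the interval length, with 12 h and 3 h as examples; protocol 9.4.5 has the same rule. It sets the AUC to missing when the last two points are missing, and explains this as needing data to 8 h for AUC0-12h and to 2 h for AUC0-3h. SAP 16.4 interpolates gaps that have readings on both sides. If only the final reading is missing, it calculates the AUC as far as the data go.

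**The concern.** The 3 h reading closes the window of the primary endpoint at its primary visit, and also the window of AUC0-3h. The faulty list stands in a derivations section, and 16.3.1 sends the reader there for peak FEV1. Programmed as written, it would give Day 1 and Week 4 fewer readings in the window than Weeks 1 to 3, although all five visits enter the same MMRM.

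The divisor gap would remain even with the list corrected. Missing final readings are foreseeable at visits lasting 12 hours, and 16.2.1.1.1 also drops readings graded unacceptable. Protocol 9.4.8 leaves AUC imputation to the SAP, so no other document settles the question. At Week 4, AUC0-12h is a key secondary endpoint (SAP 16.5).

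**Working it through.** **1. The lists side by side (post-dose hours).**

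| Visit | Protocol | SAP 16.2.1.1.1 | Readings within 0-3 h |
|---|---|---|---|
| Day 1, Week 4 | 0.5, 1, 2, 3, 4, 6, 8, 12 | 0.5, 1, 2, 4, 6, 8, 12 | 4 in protocol, 3 in SAP |
| Weeks 1 to 3 | 0.5, 1, 2, 3 | 0.5, 1, 2, 3 | 4 in both |

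Over 0-12 h on Day 1 and at Week 4 the count is 8 in the protocol and 7 in the SAP.

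**2. Which reading does the rest of the SAP presuppose?** If 2 h were the last point of AUC0-3h, losing only the last point would leave data to 1 h, and the rule would accept that. The SAP instead requires data to 2 h. The two statements agree only if 3 h is the last point. The SAP's spirometry list also equals the vital-sign times for these visits (protocol Table 4 note (d), SAP 17.4). That suggests a copying slip, which is an inference.

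**3. Divisor.** Let A be the average FEV1 over the covered time c, and L the full interval. The truncated area is A × c. Dividing by L gives A × c/L, an error of −A × (1 − c/L). Subtracting baseline leaves this error unchanged.

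- AUC0-3h with 3 h missing: c/L = 2/3 = 0.667.
- AUC0-12h with 12 h missing: c/L = 8/12 = 0.667.

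In both cases the error is −A/3. Check with a flat 1.5 L profile over 0-3 h: the full area is 4.5 L·h, and 4.5/3 = 1.5 L. Truncated at 2 h the area is 3.0 L·h; 3.0/3 = 1.0 L, whereas 3.0/2 = 1.5 L.

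This uses nominal times with pre-dose as time 0. The SAP does not say whether times are nominal or actual. With the protocol's ±15 minutes on the last available reading, c/L runs from 1.75/3 = 0.58 to 2.25/3 = 0.75 for AUC0-3h, and from 7.75/12 = 0.65 to 8.25/12 = 0.69 for AUC0-12h.

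**4. Where truncation applies.** At Weeks 1 to 3 spirometry ends at 3 h, and on Day 1 and at Week 4 it ends at 12 h. In those cases the final reading has nothing after it. A missing 3 h reading on Day 1 or at Week 4 lies between 2 h and 4 h. The SAP does not say whether the 4 h value, which is outside the window, may be used to interpolate it.

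**5. Scale, under an assumption.** The plan's sample size reproduces: n = 2 × (1.96 + 0.8416)² × 200²/93² = 72.6, so 73 per group. The documents give no mean FEV1 over these windows. Assume A between 1.0 and 1.8 L:

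- Per affected patient: −1000/3 = −333 mL to −1800/3 = −600 mL.
- On the raw mean of a 73-patient arm, per affected patient: −333/73 = −4.6 mL to −600/73 = −8.2 mL.
- Relative to 93 mL: 4.6/93 = 4.9% to 8.2/93 = 8.8%. The 93 mL was set for peak FEV1 and serves here only as a yardstick.

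**The case against.** The strongest reply is that nothing goes wrong in practice. The list says when spirometry is performed, the protocol governs collection, and SAP 3.2 defers to it. The 3 h value will be in the database. The only stated rule for peak FEV1 is defined by a window and takes that value in, and the minimum-data rule for AUC0-3h needs it. An effect would require a programmer to discard an in-window reading against all of this. That stands, and it is why the point is minor. It does not remove the contradiction within the derivation text, for which the SAP gives no order of precedence.

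A reader might infer that the primary endpoint is defined by a wrong rule, or that its treatment contrast is biased. The documents support neither. The rule in 16.1.1 and 16.1.2 matches the protocol. Even under literal programming, a patient's peak could only stay the same or fall; the effect on a within-visit contrast depends on time profiles that the documents do not give.

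A reader might also combine the two defects and conclude that every AUC0-3h on Day 1 and at Week 4 is one third too low, or that the divisor problem affects AUC0-3h at all visits. Neither follows. Truncation is a rule for missing readings, the 3 h reading is collected at those visits, and a missing one may count as bounded and be interpolated.

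On the divisor itself, 3 h and 12 h are given as examples and the result is called an average, so a programmer could reasonably divide by the time covered. That also stands: the one-third error is conditional on the literal reading.

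**Conclusion.** The point holds as two minor defects in the SAP's derivation text.

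First, the Day 1 and Week 4 list contradicts the protocol and the SAP's own AUC0-3h rule. It changes peak FEV1 and AUC0-3h only if programmed literally. No mL effect on any contrast is claimed.

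Second, truncating at the last reading while dividing by the full interval makes the affected patient's average about one third too low. This assumes the full-interval divisor, nominal times and pre-dose as time 0. It applies to AUC0-12h on Day 1 and at Week 4, and to AUC0-3h at Weeks 1 to 3. The number of affected patients is unknown, and every mL figure rests on an assumed FEV1. The error cancels in a contrast when the arms have equal numbers of affected patients with similar FEV1.

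**What to change.** Before unblinding:

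1. In SAP 16.2.1.1.1, add 3 h to the Day 1 and Week 4 list so that it matches note (h) to protocol Table 4. Peak FEV1 and AUC0-3h then use the 0.5, 1, 2 and 3 h readings at every visit.
2. In SAP 16.2.1.1.2 and 16.4, state that an AUC truncated because the final reading is missing is divided by the time actually covered: 2 h for AUC0-3h at Weeks 1 to 3, and 8 h for AUC0-12h, at nominal times.
3. In the same place, state that on Day 1 and at Week 4 a missing 3 h reading with a 4 h reading present is treated as bounded and interpolated.

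The cost is one added time point, two sentences and a check of the output shells. The protocol already schedules the 3 h reading, so no new data are needed and the sample size is unaffected.
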